5.5 Safety assessments

The Investigator will evaluate patient safety by monitoring and recording all AEs and serious adverse events (SAEs); regular monitoring of hematology, biochemistry, cardiac troponin, coagulation profile, urinalysis, pregnancy testing in women of childbearing potential, ECG, vital signs, ECOG performance status, physical examination, chest X-ray/CT; and by evaluation of concomitant medications (see schedule of assessments; Table 8 and Table 9).

Safety assessments must be performed at intervals indicated in the schedule of assessments (see Table 8 and Table 9). More frequent assessments may be performed at the Investigator's discretion, if medically indicated.

5.5.1 Eastern Cooperative Oncology Group performance status

All patients must be evaluated for ECOG performance status at Screening; prior to BAL101553 administration on Day 1 of each continuous doing treatment cycle (or within the 72 h prior to these days); and at the End of Study visit. Table 11 provides the scale to be used for these assessments.

Table 11 ECOG performance status	Table 11	ECOG 1	performance status
----------------------------------	----------	--------	--------------------

Grade	ECOG Description
0	Fully active, able to carry on all pre-disease performance without restriction
1	Restricted in physically strenuous activity but ambulatory and able to carry out work of a light or sedentary nature, e.g., light house work, office work
2	Ambulatory and capable of all self care but unable to carry out any work activities. Up and about more than 50% of waking hours
3	Capable of only limited self care, confined to bed or chair more than 50% of waking hours
4	Completely disabled. Cannot carry on any self care. Totally confined to bed or chair
5	Death

5.5.2 Adverse event monitoring

All AEs occurring from the first intake of study medication to the final assessment at follow-up must be documented on the AE CRF page, regardless of whether the event is considered to be related to the study drug or not; see Section 7.1). If possible, a diagnosis should be documented rather than signs and symptoms. All AEs must be recorded in English language.

Patients who withdraw because of a drug-related AE must be followed-up until recovery. Beyond 28 days after last study drug administration, only those procedures relevant to any remaining toxicities or AEs will be performed.

Reporting of SAEs is described in Section 7.2.3.

5.5.3 Physical examination

A complete physical examination must be performed in accordance with Table 8, or Table 9 for patients in the Phase 2a portion of the study.

Physical examination will include examination of general appearance, skin, neck (including thyroid), eyes, nose, throat, heart, lungs, abdomen, lymph nodes, extremities, and nervous system and measurement of body weight.

A patient's height must be assessed only during the Screening visit.

An AE form must be completed for changes in physical examination which are identified as clinically significant.

5.5.4 Vital signs

Vital signs include body temperature, respiratory rate, radial pulse rates, and SBPs and DBPs, and must be obtained in the same position throughout a given visit, i.e., either sitting or supine, as appropriate. Recordings are to be made after the patient has been sitting or supine for (at least) 5 min.

5.5.4.1 Phase 1

Vital signs must be performed in accordance with Table 8.

Vital signs must be obtained at Screening; on Days 1, 8, 15 and 22 of Cycles 1 and 2; on Days 1 and 15 of Cycle 3 and all subsequent cycles; and at the End of Study visit.

On Day 1 of Cycles 1 and 2, vital signs (excluding BP measurements) must be obtained pre-dose and 0.5 h, 1 h, 2 h, 3 h, 4 h, 6 h, 8 h and 24 h after intake of BAL101553 study drug; for cohorts using a q12h dosing regimen, vital signs will be also be obtained at 12 h (i.e., prior to the second daily dose) and 14 h (i.e., after the second daily dose) after first dosing on Day 1 of Cycles 1 and 2. Measurements must be obtained within the 5 min prior to PK blood sampling.

On Days 8, 15 and 22 of Cycles 1 and 2, vital signs (excluding BP measurements) must be obtained pre-dose and 0.5 h, 1 h, 2 h and 4 h after intake of BAL101553 study drug.

On Days 1 and 15 of Cycle 3 and all subsequent cycles, vital signs (excluding BP measurements) must be obtained pre-dose and 1 h after intake of BAL101553 study drug.

5.5.4.2 Phase 2a Simon's two-stage design

Vital signs must be performed in accordance with Table 9.

Vital signs must be obtained at Screening; on Days 1, 8, 15 and 22 of Cycles 1 and 2; on Days 1 and 15 of Cycle 3 and all subsequent cycles; and at the End of Study visit.

On Day 1 of Cycle 1, vital signs (excluding BP measurements) must be obtained pre-dose and 0.5 h, 1 h, 2 h, 3 h, 4 h, 6 h, 8 h and 24 h after intake of BAL101553 study drug. Measurements must be obtained within the 5 min prior to PK blood sampling.

On Day 1 of Cycle 2 and Days 8, 15 and 22 of Cycles 1 and 2, vital signs (excluding BP measurements) must be obtained pre-dose and 0.5 h, 1 h and 2 h after intake of BAL101553 study drug.

On Days 1 and 15 of Cycle 3 and all subsequent cycles, vital signs (excluding BP measurements) must be obtained pre-dose and 1 h after intake of BAL101553 study drug.

5.5.4.3 Blood pressure measurements

At Screening and at the End of Study visit, (sitting) triple BP measurements (i.e., the average of three BP measurements taken at 1–2-min intervals) will be obtained for both arms. The average of the arm with the higher triple BP will be used as the Screening BP. Details on appropriate BP measurements are outlined in Table 10.

5.5.4.3.1 Phase 1

On Days 1, 8, 15, 22 of Cycles 1 and 2, triple BP measurements (i.e., the average of three BP measurements taken at 1–2-min intervals) should be obtained for both arms pre-dose. BP measurements may be repeated if the initial SBP is \geq 140 mmHg or DBP \geq 90 mmHg. Single BP measurements should be obtained every 30 min after [first] dosing, until at least 4 h post-dose (see Section 5.5.4 and Table 10 for BP requirements for initiation and continuation of BAL101553 dosing); for cohorts using a q12h dosing regimen, single BPs will be also be obtained at 12 h and 14 h (i.e., after the second daily dose) after first dosing on Day 1 of Cycles 1 and 2. The post-dose BPs should be obtained for the arm that gave the highest pre-dose measurement. If SBP \geq 160 mmHg or DBP \geq 100 mmHg occur, triple BP should be monitored every 10–15 min until return to SBP < 160 and DBP < 100 mmHg. Patients should only be discharged home once blood pressure levels have stabilized at SBP levels < 160 mmHg and DBP levels < 100 mmHg.

On Days 1 and 15 of Cycle 3 and all subsequent cycles, triple BP measurements (i.e., the average of three BP measurements taken at 1 to 2-min intervals) should be obtained for both arms pre-dose. A single BP measurement should be obtained 1 h after [first] dosing (see Section 5.5.4 and Table 10 for BP requirements for initiation and continuation of BAL101553 dosing). The post-dose BP should be obtained for the arm that gave the highest pre-dose measurement. If SBP \geq 160 mmHg or DBP \geq 100 mmHg occurs, triple BP should be monitored every 10–15 min until return to SBP <160 mmHg and DBP < 100 mmHg. Patients should only be discharged home once blood pressure levels have stabilized at SBP levels < 160 mmHg and DBP levels < 100 mmHg.

5.5.4.3.2 Phase 2a Simon's two-stage design

Single BP measurements will be performed in the context of complete vital signs. In Cycles 1 and 2, BP should be obtained pre-dose and 0.5 h, 1 h, and 2 h after dosing, in Cycle 3 and all subsequent cycles BP should be obtained pre-dose and 1 h after dosing. BP measurements may be repeated if the initial pre-dose SBP is \geq 160 mmHg or DBP \geq 100 mmHg. If post-dose SBP \geq 160 mmHg or DBP \geq 100 mmHg occur, BP should be monitored every 10–15 min until return to SBP < 160 and DBP < 100 mmHg. Patients should only be discharged home once blood pressure levels have stabilized at SBP levels < 160 mmHg and DBP levels < 100 mmHg.

5.5.5 Electrocardiograms

5.5.5.1 Phase 1

ECGs must be performed in accordance with Table 8.

Standard, triplicate, 12-lead ECG must be performed using the pre-programmed device provided by the Sponsor. Measurements should be separated by ~1 min and be taken within a 5 min time window. During PK assessments, ECG recordings must be obtained within the 5 min prior to PK blood sampling. ECG measurements will be made at the following time points:

- Screening: to determine eligibility of patients.
- Day 1 of Cycles 1 and 2: pre-dose; 1 h, 2 h, 4 h, and 8 h after [first] BAL101553 dosing
 For cohorts using a q12h dosing regimen, triplicate ECG will be also be obtained at 14 h (i.e., after the second daily dose) after first dosing on Day 1 of Cycles 1 and 2 (Phase 1).
- Days 8 and 15 of Cycles 1 and 2: pre-dose; 2 h and 4 h after [first] BAL101553 dosing.
- Day 1 of Cycle 3 and all subsequent cycles: pre-dose.
- End of Study visit.
- Triplicate 12-lead ECG should also be obtained when patients experience SBP ≥ 180 mmHg or DBP ≥ 110 mmHg, or whenever clinical cardiovascular signs or symptoms occur.

In patients undergoing intra-patient dose escalation or dose reduction during, triplicate 12-lead ECGs must be obtained on Days 1, 8 and 15 of Cycles 1 and 2, pre-dose and 2 h and 4 h after BAL101553 dosing, at each new dose level. From the third cycle onwards, triplicate 12-lead ECGs will only be obtained pre-dose on Day 1.

ECGs performed at Screening, on Day 1 of Cycles 1 and 2, and any abnormal ECGs, will be transmitted to a central ECG laboratory for evaluation, including QTc assessment.

ECGs must always be recorded after at least 5 min rest and while the patient is in a supine or semi-supine position. ECGs must be assessed by the Investigator or his/her designee. The ECG printouts are to be signed and dated by the Investigator or his/her designee. Further instruction and training on handling the device provided and transmitting data will be provided to the study centers prior to study initiation.

The designated physician at the site must review the ECG to assess any abnormalities including prolongation of QTcF. The pre-programmed ECG device must provide automated QTcF intervals.

For an individual patient, significant prolongation of QTcF will be defined as:

- 1. Increase in the QTcF to > 500 ms, or
- 2. Increase in the QTcF of > 60 ms compared to the respective baseline.

5.5.5.2 Phase 2a Simon's two-stage design

ECGs must be performed in accordance with Table 9.

Standard, single, 12-lead ECG will be performed using local devices. During PK assessments, ECG recordings must be obtained within the 5 min prior to PK blood sampling. ECG measurements will be made at the following time points:

- Screening: to determine eligibility of patients.
- Day 1 of Cycle 1: pre-dose; 1 h, 2 h, 4 h, and 8 h after BAL101553 dosing
- Days 8 and 15 of Cycle 1, and Days 1 and 15 of Cycle 2: pre-dose, and 2 h after BAL101553 dosing.
- Day 1 of Cycle 3 and all subsequent cycles: pre-dose.
- End of Study visit.
- Single 12-lead ECG should also be obtained when patients experience SBP ≥ 180 mmHg or DBP ≥ 110 mmHg, or whenever clinical cardiovascular signs or symptoms occur.

ECG must always be recorded after at least 5 min rest and while the patient is in a supine or semi-supine position. ECG must be assessed by the Investigator or his/her designee. The ECG printouts are to be signed and dated by the Investigator or his/her designee.

The designated physician at the site must review the ECG to assess any abnormalities including prolongation of QTcF.

For an individual patient, significant prolongation of QTcF will be defined as:

- 1. Increase in the QTcF to > 500 ms, or
- 2. Increase in the QTcF of > 60 ms compared to the respective baseline.

5.5.5.3 Management of QTc prolongation or other significant ECG abnormalities

If significant QTc prolongation is observed, the patient must be monitored by the Investigator and hourly (triplicate) 12-lead ECG need to be obtained until the QTcF has returned to ≤ 470 ms and to ≤ 30 ms increase from baseline. The clinical context and possible factors contributing to QTc prolongations such as electrolyte abnormalities (potassium, calcium or magnesium), concomitant medications, or other clinical factors such as cardiac ischemia will be carefully assessed and any findings documented in the CRF. In addition, a blood sample for determination of BAL101553 concentration must be collected.

Once QTc prolongation has resolved, patients may continue treatment at a lower dose with ECG monitoring frequency as described for Cycle 1 (as in Day 1/Cycle 1 if patients continue treatment at a reduced dose within a treatment cycle). If the ECG obtained in the first cycle after dose reduction are without any QTcF intervals > 500 ms, or increase from baseline > 60 ms, then ECG monitoring in subsequent cycles may follow the normal schedule.

Patients who experience absolute QTcF > 500 ms or QTcF increase from baseline > 60 ms after dose reduction must be discontinued from study.

The clinical management in case of other ECG abnormalities is to be performed at the discretion of the Investigator. Cardiac troponin must be assessed if ECG abnormalities suggestive of cardiac ischemia are observed.

In Phase 1, all significant QTc prolongations or other relevant ECG abnormalities, must be transmitted to the central ECG reading laboratory for evaluation and confirmation.

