1.3.2.2 Oral pharmacokinetics

After repeated oral administration of BAL27862 or BAL101553 to rats and dogs, the exposure is almost dose proportional, without indication of accumulation or induction; female rats tend to be more exposed than male rats, however, this gender difference is not observed in dogs. Comparison of the exposures after oral administration of the pro-drug as a solution, with those observed after IVadministration of the drug, suggests an oral bioavailability ranging from 30–50% in the rat and 50–100% in the dog. Importantly, the oral bioavailability of BAL27862 in the rat is similar after administration of either the drug or the pro-drug. After oral administration only traces of the pro-drug are detected in plasma, suggesting a pre-systemic cleavage. These findings are in agreement with experiments in

Caco-2 cells which showed that cleavege of BAL101553 to BAL27862 occurs both in the incubation medium and intracellularly, and that BAL27862 is highly permeable.

A dedicated PK study performed in dogs, using the capsule formulation intended for clinical use, confirmed the excellent oral bioavailability of BAL101553.

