3.2.2 Dose-limiting toxicity

Whenever possible, AEs will be graded according to the National Cancer Institute CTCAE v4.03 (Phase 1) or v5.0 (Phase 2a). DLT will be defined as any one of the AEs shown in Table 5 which occur during the first 28-day treatment cycle (Cycle 1) and if considered to be at least possibly related to BAL101553.

Table 5 Overview of dose-limiting toxicities

Toxicity	CTCAE criteria
Hematological	 Grade 4 Neutropenia (ANC < 0.5 × 10⁹/L) lasting for ≥ 5 consecutive days. Febrile neutropenia (ANC < 1.0 × 10⁹/L and single temperature of > 38.3 °C, or a sustained temperature of ≥ 38.0 °C for > 1 h). Grade 4 thrombocytopenia (platelet count < 25 × 10⁹/L) or grade 3 thrombocytopenia (platelet count < 50 × 10⁹/L) with bleeding. Any other ≥ grade 4 hematological AE.
Gastrointestinal	$ullet$ \geq Grade 3 nausea, vomiting or diarrhea despite appropriate pre-medication and/or management.
Hepatic	• Grade 3 AST or ALT elevations (> $5-20 \times ULN$ or baseline if baseline was abnormal) for > 7 days, or grade 4 (> $20 \times ULN$ or baseline if baseline was abnormal) for any duration.
Cardiac	 Grade 3 QTc interval prolongation (QTcF > 500 ms or > 60 ms change from baseline). Hypertension-related DLT: Any recording of SBP > 220 mmHg or DBP > 110 mmHg; or ≥ Grade 3 Hypertension (SBP ≥ 160 mmHg or DBP ≥ 100 mmHg) that cannot be controlled to Grade 2 Hypertension within 6 weeks of initiation or modification of antihypertensive treatment; or BAL101553 treatment discontinuation due to hypertension that cannot be controlled Grade 4 Hypertension Note: The need for administration of new antihypertensive medication or modification to more intensive antihypertensive medication will not be considered as DLT.
Other AEs	 AEs leading in Phase 1 to missing > 5 doses in Cycle 1, or causing a delay in the start of Cycle 2 by > 14 days. AEs which in the view of the Investigator and/or Sponsor, represent a clinically significant hazard to the patient. Any other ≥ grade 3 non-hematological AE.
Exceptions	 The following AEs will not be considered DLT unless considered to present a clinically significant hazard to the patient: Grade 3 fatigue. Grade 3 or 4 elevations in alkaline phosphatase. Grade 3 or 4 hypophosphatemia. Grade 4 lymphopenia.

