
If, after interruption of treatment and resolution, treatment is re-initiated at the same dose level according to the criteria in Table 6, and the same toxicity reoccurs with the same severity, the next treatment re-initiation must resume at a lower dose, regardless of the duration of the toxicity.

Patients who discontinue the study due to AEs or a laboratory abnormality must be followed as described in Sections 7.2.5 and 7.2.6.

Table 6 General guidelines for treatment continuation criteria and recommendations for dose modification

	General Saldennes for th				
Type of event (CTCAE grading)	Criteria to start a new treatment cycle	Criteria to withhold dose within a cycle	Criteria to reduce dose by 1 level	Criteria to resume treatment within a cycle	Criteria to withdraw a patient from the study
General aspects	Laboratory results consistent with enrollment criteria (Section 4.2)	See criteria below	Any DLT ¹ or criteria below	Resolution of DLT¹ to ≤ CTCAE grade 1 (or baseline) and criteria below	Any drug-related event which delays new cycle by > 14 days
Specific events					
Absolute neutrophil count (ANC)	$\geq 1.5 \text{ per } 10^9/\text{L}$	$< 1.0 \text{ per } 10^9/\text{L}$	< 1.0 per 10 ⁹ /L	\geq 1.0 per 10^9 /L \geq 1.5 per 10^9 /L after DLT	(No specific criteria)
Febrile Neutropenia	None/fully resolved	Any occurrence	Any occurrence	Fully resolved	(No specific criteria)
Thrombocytopenia	$\geq 100 \text{ per } 10^9\text{/L}$	$< 50 \text{ per } 10^9/\text{L}$	$< 50 \text{ per } 10^9/\text{L}$	\geq 75 per 10^9 /L \geq 100 per 10^9 /L after DLT	(No specific criteria)
Hemoglobin	\geq 9 g/dL	< 6.5 g/dL	< 6.5 g/dL	\geq 8 g/dL	Grade 4 anemia
S-Creatinine (S-Cr)	$\leq 1.5 \times ULN$	$> 2.0 \times ULN$	$> 2.5 \times ULN$	$\leq 1.5 \times ULN$	\geq Grade 3 (S-Cr $>$ 3.0 \times ULN)
ALT/AST	$\leq 3.0 \times ULN^2$	$> 5.0 \times ULN^2$ (any duration)	$> 5.0 \times ULN^2$ for > 7 days	$\leq 3.0 \times ULN^2$	(No specific criteria)
Total bilirubin (TB)	$\leq 1.5 (2.0)^2 \times ULN^2$	$> 2.0 \times ULN^2$	$> 2.0 \times ULN^2$	$\leq 1.5 (2.0)^2 \times ULN^2$	Grade 4 (TB $> 10 \times ULN$)
Neurotoxicity ³	Grade 0 or 1	≥ Grade 2	\geq Grade 2	Grade 0 or 1	\geq Grade 3
Diarrhea ⁴	Grade 0 or 1	≥ Grade 3	\geq Grade 3	Grade 0 or 1	Grade 4
QTcF	≤ 470 ms	> 500 ms or > 60 ms change vs baseline ⁴	> 500 ms or > 60 ms change vs baseline ⁵	≤ 470 ms	Recurrent QTcF > 500 ms or > 60 ms change vs baseline

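### Table 6 and Section 5.5.5.3 of the protocol give different QTcF return limits for every baseline QTcF below 440 ms

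*Protocol*

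**What the plan says.** **Trigger.** The protocol uses the same two-limbed trigger throughout. Table 6 (Section 3.2.5.2) withholds drug at QTcF "> 500 ms or > 60 ms change vs baseline". Table 5 (Section 3.2.2) lists "Grade 3 QTc interval prolongation (QTcF > 500 ms or > 60 ms change from baseline" as a DLT, provided the event meets the general condition for DLTs, "if considered to be at least possibly related to BAL101553". Sections 5.5.5.1 and 5.5.5.2 define significant prolongation by the same two thresholds.

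**Return, Section 5.5.5.3.** Hourly ECGs continue "until the QTcF has returned to ≤ 470 ms and to ≤ 30 ms increase from baseline". The next paragraph allows treatment at a lower dose after resolution, with no further definition of resolution.

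**Return, Table 6, QTcF row.** The cells for starting a new cycle and for resuming within a cycle both say only ≤ 470 ms. The resume cell is followed directly by the withdrawal cell ("≤ 470 ms Recurrent QTcF > 500 ms"), so nothing in it refers to baseline.

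**Return, Table 6, general row.** For resuming within a cycle, a DLT must resolve "to ≤ CTCAE grade 1 (or baseline) and criteria below". Footnote 1 extends DLT to events of equal severity in later cycles. For starting a new cycle, the general row asks only for laboratory results that meet the enrollment criteria.

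**Return, Section 3.2.5.2 text.** After a DLT (Phase 1) or a DLT equivalent (Phase 2a), treatment stays interrupted until recovery to grade 1 or lower, or to baseline.

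**The concern.** The trigger can be met by the absolute value or by the change from baseline. Section 5.5.5.3 gives a return limit for both. The Table 6 QTcF cells give one only for the absolute value. Two sites, or one site opening two sections, can therefore reach different answers about whether the same patient's QTcF has returned far enough.

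In Phase 2a the sites apply these passages without a central check. Section 5.5.5.2 specifies single ECGs on local devices, and Section 5.5.5.3 sends prolongations to the central laboratory only in Phase 1. From Cycle 3 the only routine on-treatment ECG is the Day 1 pre-dose recording, which is when the new-cycle column of Table 6 applies. At stake are consistent handling of a cardiac safety signal and the comparability of the hold and re-start data that describe tolerability at the RP2D.

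**Working it through.** The plan states no figure to reproduce here; the check is on the threshold logic. Let B be baseline QTcF and Q the current reading, both in whole ms. Exclusion criterion 13 (Section 4.3) admits screening QTcF up to 470 ms, so all baselines used below are eligible.

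**Rules**
- Hold (Tables 5 and 6): Q > 500, or Q − B > 60.
- Table 6 QTcF cells, new cycle and resume: Q ≤ 470.
- Section 5.5.5.3: Q ≤ 470 and Q − B ≤ 30, that is Q ≤ min(470, B + 30).

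**Step 1: where the two return limits differ.** Section 5.5.5.3 is the tighter limit when B + 30 < 470, that is B < 440. The readings that pass the cells but not Section 5.5.5.3 run from B + 31 to 470, which is 440 − B whole-ms values.

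**Step 2: where the withhold cell and a ≤ 470 ms cell are met by one reading.** This needs B + 60 < Q ≤ 470, so B < 410. The limb above 500 ms can never overlap with ≤ 470 ms.

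| Baseline (ms) | Hold starts at | Section 5.5.5.3 limit | Pass cells, not Section 5.5.5.3 | Meet withhold cell and ≤ 470 cell |
|---|---|---|---|---|
| 380 | 441 | 410 | 411–470 | 441–470 |
| 400 | 461 | 430 | 431–470 | 461–470 |
| 409 | 470 | 439 | 440–470 | 470 |
| 410 | 471 | 440 | 441–470 | none |
| 420 | 481 | 450 | 451–470 | none |
| 439 | 500 | 469 | 470 | none |
| 440 | 501 | 470 | none | none |

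**Step 3: add the general row for resuming within a cycle.** A reading more than 60 ms above baseline is Grade 3 under Table 5, so a DLT or equivalent at that level has not recovered to grade 1 or baseline. Over integer baselines from 340 to 470 ms (131 values), none has a reading that meets the hold and the full within-cycle resume rule together. The same holds for the Section 5.5.5.3 limits: 0 of 131.

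**Step 4: what remains open at a baseline of 400 ms.**
- 431–460 ms (+31 to +60): the cells are met and Section 5.5.5.3 is not. The general row cannot be decided, because the documents give no millisecond or change-from-baseline value for QTc grade 1.
- 461–470 ms (+61 to +70), resuming within a cycle: blocked by the general row if the event is a DLT or equivalent. If it is judged not even possibly related, it is not a DLT and the general row does not apply.
- 461–470 ms, starting a new cycle: the new-cycle and withhold cells are both met, and the general row adds only laboratory results. Only the Section 3.2.5.2 text prevents dosing, and only for a DLT or equivalent.

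**The case against.** The strongest reply is that the QTcF cell is not the whole Table 6 rule. A reader who takes the cell alone might infer that a patient with a baseline below 410 ms may resume at the moment the hold is triggered. The documents do not support that for a drug-related event. The general row applies jointly with the cell, the hold thresholds are exactly the Table 5 Grade 3 thresholds, and Section 3.2.5.2 repeats the recovery condition for Phase 2a. This part of the reply stands in full.

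It does not close the gap. The general row's recovery condition sits only in the within-cycle column. It depends on relatedness, while Section 5.5.5.3 itself directs sites to look for electrolyte, concomitant-medication and ischemic causes. It also rests on a grade 1 level with no millisecond value.

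Further points on the other side:
- The 30 ms limit is written as the end of hourly monitoring. Reading it as a condition for re-starting treatment is an inference from the paragraph that follows. That is fair, but no other definition of resolution is offered.
- Footnote 5 on the reduce cell refers to Section 5.5.5, so the passages are linked. It does not restate the 30 ms limit.
- Section 3.2.5.2 calls Table 6 general guidance from which investigators may deviate, and Table 22 lists no QTc DLT in Phase 1. Both bear on priority, not on whether the passages agree.
- The sample wording ("a blood sample for determination of BAL101553 concentration must be collected") could suggest that only the pro-drug is assayed, although the protocol reports for animals that "After oral administration only traces of the pro-drug are detected in plasma". That inference goes too far: footnote 5 calls it a PK sample, and Section 5.7.1 covers BAL27862 as well as BAL101553 where applicable.

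**Conclusion.** The point holds as an internal inconsistency. The Table 6 QTcF return cells and Section 5.5.5.3 disagree for every baseline below 440 ms, by 440 − B ms (40 ms at a baseline of 400 ms). For baselines below 410 ms the new-cycle and withhold cells of the same row can be met by one reading. Within a cycle, a drug-related event still more than 60 ms above baseline cannot be resumed under the full rule.

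The conclusion rests on reading the Section 5.5.5.3 limits as the meaning of resolution. No share of affected patients can be given, because the documents do not report the distribution of baseline QTcF or how often holds occur. Nor do they show that the mismatch changes who must discontinue: the recurrence thresholds are the same in Table 6, Section 4.4 and Section 5.5.5.3. The effect is on when dosing re-starts. With no QTc DLT listed among the 54 Phase 1 patients (26 + 28), this should be corrected but is not critical. No view is taken on which limit is right.

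**What to change.** Reconcile the QTcF new-cycle and resume cells of Table 6, the recovery text in Section 3.2.5.2 and Section 5.5.5.3, so that a single return criterion addressing both limbs of the trigger appears in all of them. State whether it applies whatever the judged relatedness, and say in Section 5.5.5.3 what resolved means. The sponsor decides which limit stands.

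Two minor corrections can go in the same amendment:
- Check the footnote on the QTcF withhold cell. It reads as footnote 4, shared with the diarrhea row, while the reduce cell for the same finding carries footnote 5. This may be a slip or an effect of text extraction.
- Align the analyte named for the Section 5.5.5.3 sample with Section 5.7.1 (BAL27862, and BAL101553 if applicable).

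The cost is wording in one table row and a few sentences of a protocol amendment, with no added visits or samples.
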